measured inflammatory and tissue remodeling biomarkers at baseline and one year following mid-urethral sling in 150 women with predominant SUI. In this study, interleukin 12p70 decreased ($p = .04$) and NGF increased ($p = .03$) one year following mid-urethral sling surgery.²⁵ Furthermore, change in biomarker levels was neither associated with any clinical or demographic covariates nor surgical failure.

The shared mechanisms for SUI and UUI suggest that treatments directed at one component of MUI, either UUI or SUI, have significant potential of affecting outcomes of the other component. In MUSA, outcomes for SUI, UUI and overall UI episodes will be measured separately using both patient reported outcome (PRO) questionnaires and bladder diary, thus providing valuable data on mechanisms that contribute to the pathophysiology of MUI.

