greater reduction in total UI episodes than UUI episodes, over 6 months (-4.02 vs -3.89 episodes per day). Similarly, in the clinical responder population, women in the Botox A group reported greater reduction in total UI episodes than UUI episodes, over 6 months (-4.6 vs -4.4 episodes per day). These findings suggest that the beneficial effects of Botox A may extend beyond UUIE to total UI episodes. To further explore this, we looked at ROSETTA data for a sub-group with MUI similar to what we would recruit for MUSA to provide some preliminary data of Botox A in this urgency-predominant MUI population. There were 32 ROSETTA participants randomized to Botox A with at least moderate stress bother and moderate urge bother on the Urogenital Distress Inventory Short Form (UDI-SF) questions plus 3 or more SUIE on 3-day bladder diary (average of at least 1 per day) at baseline. UDI-SF scores at baseline were worse in the “MUSA-like” group than the rest of the ROSETTA population (75.2 vs 58.2). Similarly, average daily total UIE (8.0 vs 5.7), UUIE (6.0 vs 5.5) and SUIE (1.8 vs 0.2) were higher in the “MUSA-like” group than the rest of the ROSETTA population. This supports the conceptual framework that MUI is a more severe condition than UUI alone. At 6 months, the “MUSA-like” group had a reduction of -1.1 SUIE/day (58% improvement) and -4.0 UUIE/day (66% improvement) with Botox A; the rest of the ROSETTA population had reduction of -3.4 UUIE/day (66% improvement). These findings suggest that the beneficial effects of Botox A may extend beyond UUIE to SUIE in women with MUI.

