4.1 Eligibility Criteria/Rationale for Inclusion/Exclusion

4.1.1 Defining the MUSA MUI Population

The MUSA population consists of women with bothersome MUI. Women in MUSA must report subjectively bothersome SUI and UUI and must also objectively demonstrate SUI and UUI. In determining eligibility criteria, the protocol committee considered the ultimate goal of MUSA. The population of MUSA are women with MUI who would benefit from either Botox A or mid-urethral sling but it is unclear whether treatment should begin with Botox A or mid-urethral sling. Therefore, participants must have bothersome

symptoms, however, criteria are not so strict that women on either the moderate or severe end of the spectrum are excluded or recruitment is hindered (as was in MIMOSA).

A single instrument that provides objective documentation of both SUI and UUI does not exist. A bladder diary allows documentation of both conditions; however, women are frequently unable to clearly characterize a leakage episode as SUI or UUI. Similarly, more invasive UDE testing also allows objective documentation of SUI and detrusor overactivity (DO) but DO correlates poorly with OAB symptoms and UDE does not predict treatment outcomes of either SUI or UUI.⁹⁰⁻⁹³ Therefore, similar to ESTEEM, MUSA will use a variety of instruments to identify women with MUI who have both subjective and objective evidence of MUI. This includes subjective documentation of at least moderately bothersome SUI and UUI on a PRO (UDI), objective documentation of UUI on bladder diary, and objective documentation of SUI by CST or UDE.

Rationale for Bladder diary criteria for MUSA

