In determining the number of episodes required on bladder diary for inclusion into MUSA, the protocol committee reviewed bladder diary criteria for existing SUI and UUI trials (see tables 1 and 2 on Botox and mid-urethral sling). SUI trials typically have not used a bladder diary inclusion criterion; objective criteria of SUI is met by CST or UDE. Most Botox A trials have specified the number of UUI episodes in their inclusion criteria. The ESTEEM trial has shown that worse OAB (DO on urodynamics, previous OAB medication use, and for the sling only group, higher baseline UDI irritative subscore) is a predictor of failure to treatment, based on combined subjective (not meeting MCID for UDI-total score) and objective (not achieving >70% improvement on mean IE/day or additional SUI / UUI treatment) criteria. The team decided that at least 4 UUI episodes on a 3-day diary would be appropriate for documenting objective UUI and allow recruitment of a MUI population with higher UUI bother than ESTEEM while not necessarily being UUI-predominant. In ESTEEM, 70% of participants at baseline had at least 4 UUIE in 3 days (≥ 1.3 UUIE/day on average); this population had a mean 3.7 UUIE/day, 2.5 SUIE/day, 6.6 total UIE/day, 70 UDI-irritative score, and 85 UDI-stress score and an overall 20% failure rate at 3 months. The number of UUI incontinence episodes has purposefully not been set as high as previous Botox trials (Table 1) because the MUSA population is not limited to a refractory UUI or UUI-predominant population and to allow recruitment of a broad spectrum of women with MUI. Additionally, MUSA's primary outcome is not defined by diary improvement.

Rationale for Urodynamic evaluation inclusion criteria for MUSA

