Change from baseline in Urge Incontinence Episodes at 6 months (and at 3 and 12 months)	Continuous	The daily frequency of urge incontinence episodes will be taken from the bladder diary. The outcome will then be computed as the difference in daily frequency of urge incontinence episodes at 6 months (and 3 and 12 months) and the daily frequency of urge incontinence episodes at baseline. If data for the assessment time point are missing, the outcome variable will be coded as missing.
Change from baseline in Stress Incontinence Episodes at 6 months (and at 3 and 12 months)	Continuous	The daily frequency of stress incontinence episodes will be taken from the bladder diary. The outcome will then be computed as the difference in daily frequency of stress incontinence episodes at 6 months (and 3 and 12 months) and the daily frequency of stress incontinence episodes at baseline. If data for the assessment time point are missing, the outcome variable will be coded as missing.
Change from baseline in Mixed or Don't Know Incontinence Episodes at 6 months (and at 3 and 12 months)	Continuous	The daily frequency of mixed urge and stress incontinence episodes will be taken from the bladder diary. The outcome will then be computed as the difference in daily frequency of mixed incontinence (noted on diary as "both stress/urge") or "don't know" episodes at 6 months (and 3 and 12 months) and the daily frequency of mixed incontinence episodes at baseline. If data for the assessment time point are missing, the outcome variable will be coded as missing.
Change from baseline in Total Incontinence Episodes at 6 months (and at 3 and 12 months)	Continuous	The daily frequency of total incontinence episodes will be taken from the bladder diary. The outcome will then be computed as the difference in daily frequency of total incontinence episodes at 6 months (and 3 and 12 months) and the daily frequency of total incontinence episodes at baseline. If data for the assessment time point are missing, the outcome variable will be coded as missing.

Variable	Туре	Definition				

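### SAP 9.2 does not say whether diary leaks marked 'both stress/urge' also count as urge and stress episodes; if they do not, a persisting 'both' leak can move into the off-target count

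*SAP*

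**What the plan says.** SAP 9.2 lists four episode outcomes from the diary, each as a change from baseline at 3, 6 and 12 months:

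- Urge: "The daily frequency of urge incontinence episodes will be taken from the bladder diary".
- Stress: "The daily frequency of stress incontinence episodes will be taken from the bladder diary".
- A separate row headed "Change from baseline in Mixed or Don't Know Incontinence Episodes at 6 months (and at 3 and 12 months"), which takes leaks the diary records as both stress and urge and pools them with 'don't know' leaks. Its definition is uneven: the follow-up count names both kinds, the baseline count only the mixed kind.
- Total: "The daily frequency of total incontinence episodes will be taken from the bladder diary".

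Neither the urge nor the stress row gives a rule for 'both' leaks.

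Protocol 2.2.1 says that "outcomes for SUI, UUI and overall UI episodes will be measured separately", by questionnaire and by diary. Protocol 4.1.1 acknowledges that "women are frequently unable to clearly characterize a leakage episode as SUI or UUI". The diary outcomes are exploratory (Protocol 1.2, SAP 3.2.3), and their p-values are descriptive (Protocol 6.2.3, SAP 7.8).

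**The concern.** A 'both' leak has an urgency element and a stress element. If it sits only in the mixed row, it is in neither component count at baseline. Suppose a sling removes the stress element and the leak still occurs with urgency: at follow-up it is labelled urge and enters the urge count as if new. After Botox the same thing can happen in the stress count.

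The relabelling is a consequence of treatment, so randomisation does not remove it. The two treatments target different components, so it acts on urge in one arm and on stress in the other. What is at stake is the diary's reading of the off-target component: whether urge leaks improve or worsen after a sling, and whether stress leaks improve after Botox.

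**Working it through.** The plan gives no figure of its own on this point. The check has four parts.

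**1. How many leaks could move?** If labels are exclusive, residual = total − urge − stress, which is 'both' plus 'don't know'.

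- ESTEEM women with at least 4 urge episodes in 3 days (Protocol 4.1.1: "this population had a mean 3.7 UUIE/day, 2.5 SUIE/day, 6.6 total UIE/day"): 6.6 − 3.7 − 2.5 = 0.4/day, or 0.4/6.6 = 6% of leaks. Rounding of the three inputs allows 0.25 to 0.55.
- ROSETTA 'MUSA-like' women against the rest (Protocol 2.4: "average daily total UIE (8.0 vs 5.7), UUIE (6.0 vs 5.5) and SUIE (1.8 vs 0.2) were higher"): 8.0 − 6.0 − 1.8 = 0.2/day, or 2.5% of leaks (rounding range 0.05 to 0.35). For the rest, 5.7 − 5.5 − 0.2 = 0.0.

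Urge plus stress never exceeds total, which fits exclusive labels. It does not prove them: 'both' leaks counted twice and offset by 'don't know' leaks would give the same sums.

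**2. What does the counting rule do?** Assumed diary, per day: 2 urge-only, 1 stress-only, B 'both'. The sling removes all stress. Exclusive count = urge-only; inclusive count = urge-only + 'both'. Change in urge episodes per day:

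| B | All 'both' persist as urge: exclusive / inclusive | Same, and urge leaks fall 25%: exclusive / inclusive | 'Both' leaks vanish: exclusive / inclusive |
|---|---|---|---|
| 0 | 0 / 0 | −0.50 / −0.50 | 0 / 0 |
| 0.2 | +0.2 / 0 | −0.35 / −0.55 | 0 / −0.2 |
| 0.4 | +0.4 / 0 | −0.20 / −0.60 | 0 / −0.4 |
| 1 | +1.0 / 0 | +0.25 / −0.75 | 0 / −1.0 |

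Example, third column, B = 0.4: follow-up urge = 0.75 × (2 + 0.4) = 1.8; exclusive 1.8 − 2 = −0.20; inclusive 1.8 − 2.4 = −0.60.

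The mirror case (Botox removes all urgency, every 'both' leak persists as stress) gives a stress change of (1 + B) − 1 = +B exclusive and (1 + B) − (1 + B) = 0 inclusive.

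B = 1 is 1/4 = 25% of this diary's leaks, far above the cited averages. It stands for an individual woman with many 'both' leaks, not for a mean.

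**3. When does a net rise appear?** If a fraction f of the U single-type leaks disappears and all B persist, the exclusive change is −fU + B. It is positive only if f < B/U.

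- Urge after sling, ESTEEM subgroup counts: 0.4/3.7 = 11%.
- Stress after Botox, ROSETTA MUSA-like counts: 0.2/1.8 = 11%.

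A fall above about 11% in single-type leaks therefore turns a mean rise into a muted fall.

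**4. Do the other rows reveal it?** Only in part. Inclusive urge change = urge change + 'both' change, but the mixed row gives 'both' change + 'don't know' change. Take urge +0.4 and mixed −0.4. If the mixed fall is all 'both', leaks with urgency changed by +0.4 − 0.4 = 0. If it is all 'don't know', they changed by +0.4. The total row does not depend on labels, so it cannot say which component changed.

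**The case against.** The strongest reply is that the SAP nowhere excludes 'both' leaks. A reader might infer that it does, but this comes only from the separate row, and the diary form and its scoring instructions are not in the documents. That stands, and it is why the point is a missing rule rather than a wrong one.

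A reader might also infer that cure of one component is automatically scored as worsening of the other. The documents do not support that. Protocol 2.2.1 argues for shared mechanisms, so some 'both' leaks may simply stop. In the cited data the off-target counts fell: urge by 0.57/day at 6 months and 0.38/day at 12 months in the ESTEEM sling-only arm (Protocol Table 7), and stress by 1.1/day, or 58%, on Botox in the ROSETTA MUSA-like group (Protocol 2.4). Relabelling may have shrunk those falls, but no net rise appears.

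A third tempting step is to set 0.4 against 0.57 and call the distortion 70% of the sling's urge effect. That divides a baseline residual from a subgroup by a change in the whole arm. It also needs every residual leak to be 'both', stress cured in every woman, and every such leak to persist as urge.

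Nor does the trial rest its question about the untargeted component on the diary. Protocol 3.4.2 assigns component outcomes to the UDI-irritative and UDI-stress subscales, and Protocol 3.4.1.a calls diaries less reliable in mixed incontinence, particularly for stress leaks.

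Finally, inclusive counting is not neutral. The last column of the table shows it crediting the sling with an urge reduction when a 'both' leak disappears because its stress element was cured. That is a good reason to add inclusive counts rather than substitute them.

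**Conclusion.** The concern holds as a gap in definition with a possible, arm-specific bias. If labels are exclusive, the off-target change can be understated, and in women with many persisting 'both' leaks it can show a false rise: urge after sling, stress after Botox. The mean shift is capped at about 0.2/day (ROSETTA MUSA-like) to 0.4/day (ESTEEM subgroup). The cap is reached only if every residual leak is 'both' and persists as a single-type leak. The frequency of 'both' leaks in MUSA itself is not given, so the actual size is unknown. If 'both' leaks are already counted in each component, this bias does not arise, but the rule still needs to be written. The UDI primary and secondary outcomes and the total-episode count are unaffected. This is a cheap improvement to exploratory outcomes and no threat to the main conclusion.

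**What to change.** In SAP 9.2:

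1. State that the urge and stress episode counts use exclusive labels.
2. Add a sensitivity analysis of the same change-from-baseline outcomes, with the same model, using inclusive counts (urge + 'both'; stress + 'both') at baseline and follow-up alike.
3. Tabulate 'both' and 'don't know' separately, and word the baseline and follow-up parts of the mixed row the same way.
4. State that an off-target rise or muted fall in the exclusive counts will be interpreted only alongside the inclusive counts.

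The exclusive counts stay as the main definition, which keeps comparability with earlier trials. The cost is a few lines of text and one derivation line per outcome; SAP 9.2 indicates that the diary already records the labels. There are two small downsides: inclusive counts do not add up to the total, and 'don't know' leaks may still be relabelled once one component is cured.

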9.4 Analysis Methods for secondary and exploratory outcomes

There are three secondary outcomes for the primary aim. The mean change from baseline in UDIstress and UDI-irritative subscores will be compared between groups at 6 months, and the UDI total will be compared at 3 months (see above). The statistical analysis of the three secondary outcomes will be identical to the primary analysis described above for the UDI total score. In addition, the per-protocol analysis will be repeated for the secondary outcomes.

For all continuous exploratory measures, groups will be compared using the same model as the primary analysis described above for the UDI total score.

For any dichotomous outcomes assessed across time, groups will be compared for the odds of the event, and an odds ratio will be estimated from a repeated measures logistic generalized linear regression model with adjustment for baseline value, site and baseline age category, and with treatment, visit and treatment by visit interaction with an unstructured covariance pattern separately within each treatment group for the within-subject repeated measures.

For PGI-I and PGSC, the baseline PGI-S score will be the baseline covariate.

Example code from SAS to produce this analysis is as follows:

```
Proc glimmix;
  class subjectID trtgrp VISIT site;
  model dep_var = bbaseline_var trtgrp site visit trgrp*visit /
      solution link=logit dist=binary oddsratio DDFM=KR;
  random time / type=UN Group=trtgrp subject=subjectID RSIDE;
  lsmeans trtgrp*time / ILINK CL; /*estimates event rates*/
  lsmeans trtgrp*time / oddsratio diff CL; /*estimates ORs*/
  estimate `trt a vs trt b at time 2' trtgrp 1 -1 trtgrp*time 0 1 0 0 0 -10 0 / EXP CL;
Run;
```

Groups will be compared for receipt of additional treatment with chi-squared tests or Fisher's exact test for small event rates.

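### The mixed-or-don't-know diary outcome leaves don't-know episodes out of its baseline term, so its within-arm change is shifted toward worsening for women who recorded any at baseline (low priority)

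*SAP*

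**What the plan says.** The row in SAP 9.2 (Variable Definitions) is titled "Change from baseline in Mixed or Don't Know Incontinence Episodes at 6 months (and at 3 and 12 months"). It opens with the sentence "The daily frequency of mixed urge and stress incontinence episodes will be taken from the bladder diary", which does not name don't-know episodes.

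The formula's follow-up term reads "difference in daily frequency of mixed incontinence (noted on diary as 'both stress/urge') or 'don't know' episodes at 6 months", so it counts two diary responses. The formula then closes with "episodes at 6 months (and 3 and 12 months) and the daily frequency of mixed incontinence episodes at baseline", where the subtracted term names mixed episodes only. The gloss in the follow-up term ties the word mixed to one diary response, leakage of both types, and names don't know as a separate response.

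The other diary-count rows repeat one category on both sides of the difference. The total-episode row, for instance, uses "daily frequency of total incontinence episodes at 6 months (and 3 and 12 months) and the daily frequency of total incontinence episodes at baseline". The urge, stress, nocturnal-void and diurnal-void rows do the same.

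SAP 9.4 sets the analysis: "For all continuous exploratory measures, groups will be compared using the same model as the primary analysis". SAP 7.2 adds that the baseline value of the outcome variable is a covariate in models of change from baseline. SAP 7.8 makes p-values for exploratory outcomes descriptive only.

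**The concern.** A change from baseline should count the same thing at both times. Here one kind of episode is in the follow-up count and missing from the baseline count. A woman who records don't-know episodes at baseline and has exactly the same diary at 6 months would get a positive change, which reads as worsening. A woman whose don't-know leaks stop while her mixed leaks continue would get zero, which reads as no improvement.

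The category has clinical relevance in this trial. Protocol 2.2 notes that many women with MUI do not describe clear-cut stress or urgency leakage, and Protocol 4.1.1 says women often cannot classify a leak when completing the diary. At stake are the reported within-arm mean changes for this one diary category and the baseline covariate in its model.

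**Working it through.** The documents state no power, threshold or expected value for this outcome, so there is no planned figure to reproduce. The check is arithmetic on the definition.

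**Definition.** Let M be mixed episodes per day, D don't-know episodes per day, bl baseline and fu follow-up. Change is follow-up minus baseline, so positive means worse.

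- As written: (M_fu + D_fu) − M_bl
- Same category on both sides: (M_fu + D_fu) − (M_bl + D_bl)
- Difference between the two: +D_bl, which is never negative and is zero for a woman with no don't-know episode at baseline.

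**Worked diaries (3 days; counts are mixed + don't know).**

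| Baseline | Follow-up | As written, per day | Consistent, per day |
|---|---|---|---|
| 2 + 0 | 2 + 0 | 2/3 − 2/3 = 0 | 0 |
| 2 + 1 | 2 + 1 | 3/3 − 2/3 = +0.33 | 0 |
| 1 + 3 | 1 + 3 | 4/3 − 1/3 = +1.00 | 0 |
| 2 + 1 | 2 + 0 | 2/3 − 2/3 = 0 | 2/3 − 3/3 = −0.33 |

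**Average size.** The mean shift in an arm is the mean of D_bl, which the documents do not give. An outer scale can be taken from prior-trial baseline means in the protocol, assuming that urge, stress and mixed-or-don't-know episodes are exclusive and sum to the total:

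- ESTEEM women with at least 4 urgency episodes in 3 days (Protocol 4.1.1: "this population had a mean 3.7 UUIE/day, 2.5 SUIE/day, 6.6 total UIE/day"): 6.6 − 3.7 − 2.5 = 0.4/day.
- ROSETTA women resembling the MUSA population (Protocol 2.4): 8.0 − 6.0 − 1.8 = 0.2/day.

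The share of this category that is don't know is also not given. Over the full range:

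| Share don't know (assumed) | Shift if category is 0.4/day | Shift if category is 0.2/day |
|---|---|---|
| 0% | 0 | 0 |
| 25% | 0.1 | 0.05 |
| 50% | 0.2 | 0.1 |
| 75% | 0.3 | 0.15 |
| 100% | 0.4 | 0.2 |

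**Effect on the treatment comparison.** D_bl is fixed before randomization, so its expectation is the same in both arms and it cancels from the between-arm difference on average. What remains is precision: the model adjusts for M_bl where it could adjust for M_bl + D_bl.

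A null simulation illustrates this, using 69 women per arm, 4,000 replicates, assumed Poisson-gamma counts averaging 0.2/day for each kind, no change over time, and a single-visit analysis of covariance. Mean change was +0.20/day as written and 0.00 with the consistent definition. The adjusted treatment difference was close to zero under both (−0.002 and −0.001), with mean standard errors of 0.081 and 0.076.

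**The case against.** The strongest reply is that this is a wording slip. The title says mixed or don't know, and a change from baseline in a named category means that category at both visits. The lead sentence, taken literally, would drop don't-know episodes at follow-up too, so mixed may simply be shorthand for the titled category. SAP 7.2 also takes the covariate to be the baseline value of the outcome variable, which carries that title. This reading is plausible. But the only formula given says otherwise, nothing else in the protocol or SAP supplies the baseline term, and a programmer following the row would compute the mismatch.

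A second reply is that the size is largely unknown, and this stands. The protocol sections used for scale report total, urge and stress means without saying that the types are exclusive. Those means are rounded to 0.1, so three of them can move each residual by up to 0.15: 0.25 to 0.55 for ESTEEM and 0.05 to 0.35 for the MUSA-like ROSETTA group. The same subtraction in the remaining ROSETTA women gives 5.7 − 5.5 − 0.2 = 0.0. No single figure for the shift can be defended.

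A third reply is that nothing important rests on the row. It is exploratory with descriptive p-values, and SAP 3.2.3 lists incontinence episodes on the diary without naming this sub-category. This also stands, and it sets the priority.

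**Conclusion.** The definition is wrong as written and should be corrected, at low priority. Followed literally, it shifts each woman's change upward by exactly her baseline don't-know rate, understates mean improvement in this category in both arms, and leaves those episodes out of the covariate. The average shift is unknown. It lies between zero and the size of the whole category, roughly 0.2 to 0.4/day if diary types are exclusive and sum to the total and the cited prior-trial groups are a fair guide.

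Three stronger conclusions that a reader might draw are not supported:

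- **Every unchanged woman is scored as worse.** Only a woman with at least one don't-know episode at baseline is affected; otherwise she scores 0.
- **The comparison of Botox A with sling is biased.** The shift comes from a pre-randomization count, so the between-arm difference is unbiased on average and at most slightly less precise. The size of that precision loss rests on assumed count distributions.
- **Improvement in leaks that women cannot classify is lost to the trial.** Such leaks are part of the total-episode outcome, which is consistently defined, and Protocol 3.4.1 says the UDI has items not specific to stress or urgency.

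The primary outcome, the three secondary outcomes, and the urge, stress and total-episode outcomes are unaffected.

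**What to change.** In SAP 9.2, define this variable at every visit, baseline included, as the number of mixed episodes (the diary response for both stress and urge) plus don't-know episodes, divided by the number of diary days. Change is then that sum at 3, 6 or 12 months minus the same sum at baseline. State that the same baseline sum is the covariate under SAP 7.2 and 9.4, and reword the row's lead sentence to name both kinds.

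The cost is a sentence or two in the SAP and a check that the derivation program matches. No new data are needed, provided that the baseline diary offers the same response options as the follow-up diaries; the documents describe no separate baseline version.
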